**Abbreviations**

Abbreviation	Definition
AlkP	alkaline phosphatase
ALT	alanine aminotransferase
AMA	anti-mitochondrial antibody
ANA	antinuclear antibody
Anti-LKM1	anti-liver kidney microsomal antibody type 1
ASMA	anti-smooth muscle antibodies
AST	aspartate aminotransferase
BMI	body mass index
CBC	complete blood count
CHF	congestive heart failure
CMV	cytomegalovirus
[REDACTED]	[REDACTED]
CT	computerized tomography
DM	diabetes mellitus
DNA	deoxyribonucleic acid
EBV	Epstein-Barr virus
ERCP	endoscopic retrograde cholangiopancreatography
ESR	erythrocyte sedimentation rate
EOI	end of intervention
GGT	gamma-glutamyltransferase
HAV	hepatitis A virus
HBsAg	hepatitis B surface antigen
HCV	hepatitis C virus
HepB	hepatitis B virus
HEV	hepatitis E virus
IgM	immunoglobulin M
INR	international normalized ratio
LT/LFT	liver tests/liver function tests
MRI	magnetic resonance imaging
MRCP	magnetic resonance cholangiopancreatography
NSAID	nonsteroidal anti-inflammatory drug
OTC	over the counter
PT	prothrombin time
PTT	partial thromboplastin time
RNA	ribonucleic acid
Tbili	total bilirubin
TIBC	total iron binding capacity
ULN	upper limit of normal
WBC	white blood count

## **APPENDIX 7. SPONSOR GUIDANCE ON STUDY CONDUCT DURING THE CORONAVIRUS DISEASE 2019 (COVID-19) PANDEMIC**

Every effort should be made to adhere to protocol-specified assessments for participants on study drug including follow-up, to the extent possible. However, the sponsor recognizes that the COVID-19 pandemic may have an impact on the conduct of this clinical study including, but not limited to: self-isolation or quarantine by study participants and study-site personnel, travel restrictions and limited access to public places (including hospitals), and study site personnel being reassigned to critical tasks. Thus, while aligning with recent health authority guidances, the sponsor is providing options for managing study participants in the event of a disruption to the conduct of the study due to the COVID-19 pandemic. This sponsor guidance does not supersede local or government guidelines, requirements, or the clinical judgement of the investigator. Protecting the safety, welfare, and rights of study participants must be of utmost priority. If a participant's safety is at risk, study drug should be discontinued at the discretion of the investigator, and study follow-up should be conducted. The sponsor will continue to monitor the conduct and progress of the clinical study, and any changes will be communicated to the sites and to the health authorities according to local guidance. If a participant has confirmed or suspected COVID-19, the investigator should contact the Medical Monitor to discuss plans for study drug and follow-up and report as an AE.

### **Measures Considered**

Protocol-required visits to the clinical site may not be possible during the COVID-19 pandemic. Hence, temporary measures may be implemented, if deemed appropriate by the sponsor and investigator, to maintain continuity of participant care and study integrity. Certain measures, including but not limited to, those listed below, may be necessary and should be taken in accordance with applicable laws, regulations, guidelines, and procedures:

- Virtual or remote (e.g., by phone/telemedicine) and/or off-site (e.g., in-home) interactions between site staff (or designees) and participants for study procedures such as those related to safety monitoring, efficacy evaluation, and study drug administration (including training where pertinent).
  - Conduct interview with participants to collect safety data and include questions regarding general health status.

[REDACTED]

- Procurement of study drug by participants (or designee) from the site or shipment of study drug directly to participants for at home administration.
- Laboratory assessments using a suitably accredited local laboratory; for selected assessments such as urine pregnancy, home testing may be conducted.

### **COVID-19-Related Exclusion**

The field of COVID-19-related testing (for presence of, and immunity to, the SARS-CoV-2 virus) is rapidly evolving. Additional testing may be performed as part of Day 1 and/or during the study if deemed necessary by the investigator and in accordance with current regulations or guidance from authorities and standards of care.

### **Documentation**

Document what relevant contingency measures are implemented, how restrictions related to COVID-19 led to changes to the study conduct, and how the study participant was impacted. Related documentation, either in source or systems (e.g., eCRF), should be labelled with the prefix “CV19.” Protocol deviations related to the pandemic should also be labeled as such with the “CV19” prefix.

Activities that require the appropriate documentation include, but are not limited to, the following:

- Missed, delayed, or modified visits and/or assessments;
- Study drug dosing modification, dosing interruptions, and discontinuation and withdrawal from the study;
- Other temporary measures such as those listed in this appendix;
- If a participant is excluded from the study due to recent COVID-19-related elements, the reason for screen failure should be documented in the CRF.

1. INTRODUCTION

This statistical analysis plan (SAP) outlines the planned summarization and analysis of clinical data collected in the long-term safety (LTS) study of Protocol 0164 for TD-1473. Specifications for tables, figures, and data listings are contained in a separate document.

The results of the planned analyses will be presented in a synoptic clinical study report (CSR) which will include analyses of study subject data and safety endpoints. Inferential statistical tests will not be performed. The protocol-planned efficacy analyses will be excluded as they are not necessary for a synoptic CSR.

The 0164 study was terminated early due to lack of efficacy in the 0157 study, for all subjects the date of last dose occurred by 09SEP2021 and the end of study visit by 11OCT2021.

The analysis of pharmacokinetics data (derivation and summarization of individual PK parameters) is outside the scope of this document and is not addressed here.

This document describes the a priori plan for analysis. Any substantive modification to this analysis plan will be identified in the CSR.

Information in the appendices to the SAP are not considered a formal section of the signed SAP.

1.1. Objectives and Endpoints

1.1.1. Primary Objective

The primary objective of the study is as follows:

- To assess the safety and tolerability of TD-1473 administered up to 3 years in subjects with moderate to severe ulcerative colitis (UC) after participation in the Maintenance Study of Protocol 0157.

1.1.2. Secondary Objective

Not applicable for the synoptic CSR.

1.1.3. Exploratory Objectives

Not applicable for the synoptic CSR.

1.2. Study Design

This LTS Study 0164 will utilize a multi-center, parallel-group design to evaluate the safety of long-term TD-1473 treatment in subjects with moderate to severe UC rolling over from Protocol 0157 for up to 3 years.

Subjects eligible for the study are those who are rolling over from Protocol 0157 Maintenance Study who meet all inclusion and no exclusion criteria, including having achieved clinical response during an Induction Study and during the Maintenance Study who:

- a) demonstrate persistent [REDACTED] loss of response (no improvement for approximately 6 to 8 weeks after meeting loss of response criteria despite more time on study drug and potentially concurrent rescue medication)

OR

- b) have repeated (two) Clinical Flares after an episode [REDACTED]
[REDACTED]

OR

- c) complete the Maintenance Study and confirmation of clinical remission status results are available [REDACTED]
[REDACTED]

All subjects will receive active drug at three dose levels of 20 mg, 80 mg and 200 mg, and thus, this study will not be placebo-controlled, but blinding as to the specific dose of TD-1473 will be maintained. The dosing regimen for subjects ([Table 3](#)) entering the Long-Term Study from the Maintenance Study will be based on:

1. The subject's clinical remission status from Protocol 0157 upon entry into the LTS Study
2. The subject's study drug assignment during the Protocol 0157 Maintenance Study.

[figure not shown]
Subjects entering the LTS Study after completing the Maintenance Study in clinical remission on active drug will continue with the same dose of TD-1473. Subjects entering the LTS Study after completing the Maintenance Study in clinical remission on placebo will be placed on 20 mg.

Subjects who enter the LTS Study not in clinical remission on TD-1473 upon completion of the Maintenance Study and subjects who exit the Maintenance study prematurely due to persistent loss of response or recurrent clinical flare with loss of response (also not in clinical remission) will receive an escalated dose in the LTS Study, based on their Maintenance Dose. Subjects on 20 mg and 80 mg of TD-1473 will be dose-escalated one level up to 80 mg and 200 mg, respectively. Subjects on the highest dose (200 mg) will remain on the highest dose. Placebo subjects entering the LTS Study not in remission will be dose escalated to 80 mg.

The dose assigned to subjects entering the LTS is thus partially dependent on the clinical remission status upon entry. For subjects completing the Maintenance Study in remission on active drug, continuing on the same dosing regimen will potentially allow for maintenance of clinical benefit and continued assessments for maintenance of response/remission. For subjects on TD-1473 entering LTS with persistent loss of response or recurrent clinical flare after loss of response, dose escalation in LTS may allow for the possibility of achieving clinical benefit and even recapture of clinical response at a potentially higher dose than that administered during the Maintenance Study. For placebo subjects entering LTS not in clinical remission, dose escalation to 80 mg would potentially allow for achievement of clinical response or remission. For placebo subjects entering LTS in clinical remission, escalation to 20 mg would potentially allow for a higher likelihood of maintenance of clinical remission.

After the global, last subject study visit (including the 4 week follow up visit), an analysis of safety data will be performed.

No interim analyses are planned for this study.

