**Coexisting medical conditions or past medical history:**

6. Deemed by the investigator to be inappropriate for this study; or has any condition which would confound or interfere with the evaluation of the safety or tolerability of the study drug [e.g., developed unstable or uncontrolled and clinically significant allergic (except for untreated, asymptomatic, seasonal allergies), hematological, endocrine/metabolic, coagulation, immunologic, pulmonary, cardiovascular, hepatic (except hepatic steatohepatitis), GI (except UC), genitourinary, psychiatric, oncologic thrombotic (e.g., deep vein thromboses (DVT) or pulmonary embolism or neurological disease or other medical disorder before during or after Protocol 0157)]; or is unable or unwilling to comply with the study protocol.
7. Develops hypersensitivity to excipients or contents of the study drug as noted in Protocol 0157.
8. Participating in or interested in participating in another investigational study (exception Protocol 0157)
9. Has clinically significant abnormalities in the results of laboratory evaluations at the most recent laboratory evaluation prior to LTS Day 1 visit as determined by the investigator, including:
  - AST, ALT, or alkaline phosphatase  $\geq 2x$  the upper limit of normal (ULN)
  - Total bilirubin  $> 2x$  ULN (unless diagnosis of Gilbert's syndrome)
  - Creatinine clearance as calculated by the Cockcroft-Gault formula  $< 30$  mL/min (Refer to [Appendix 2](#))
  - Total white blood cell count (WBC)  $< 3 \times 10^9/L$
  - Absolute neutrophil count  $< 1.5 \times 10^9/L$
  - Absolute lymphocyte count  $< 0.8 \times 10^9/L$
  - Hemoglobin  $< 8$  g/dL
  - Platelet count  $< 100 \times 10^9/L$ .
10. Subject has had a live viral vaccine (e.g., MMR, varicella zoster, herpes zoster, oral polio virus, FluMist®, attenuated typhoid fever vaccine, attenuated rotavirus vaccine, yellow fever vaccine, or any investigational live vaccine) within 4 weeks prior to Day 1 and/or is unwilling or unable to avoid live viral vaccines during the Study and for 8 weeks following the last dose of study drug. Subject must be willing to avoid contact with any

household member who has been vaccinated with a live attenuated vaccine within 2 weeks after vaccination.

11. Are pregnant, lactating, breastfeeding or planning to become pregnant during the Study or within 7 days after the last dose of Study Drug

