### 8.4.2. Disposition

An enrollment summary will be provided showing the following counts by previous study treatment and clinical status at enrollment:

- Number of subjects eligible to enroll
- Number who elected to enroll
- Number who received at least one LTS dose

Enrollment will also be summarized for subjects in the Safety analysis set by region and country, and by site, ordering sites by descending number of subjects dosed.

For subjects in the Safety analysis set, a disposition summary will present the following counts:

- Number of subjects who completed the Week 4 visit
- Number who completed the Week 12 visit
- Number who completed the Week 52 (1-yr) visit
- Number who completed the Week 104 (2-yr) visit
- Number who completed the Week 156 visit
- Number who discontinued from the study prior to the Week 156 visit, overall and by reason for discontinuation

Subjects who discontinue study drug prior to the Week 156 visit will complete an End of Study visit 4 weeks after their last dose of study drug.

[REDACTED]

[REDACTED]

[REDACTED]

[REDACTED]

[REDACTED]

[REDACTED]

[REDACTED]

[REDACTED]

[REDACTED]

[REDACTED]

[REDACTED]

[REDACTED]

[REDACTED]

[REDACTED]	[REDACTED]	[REDACTED]
[REDACTED]	[REDACTED]	[REDACTED]
[REDACTED]	[REDACTED]	[REDACTED]
[REDACTED]	[REDACTED]	[REDACTED]

[REDACTED]	[REDACTED]	[REDACTED]
[REDACTED]	[REDACTED]	[REDACTED]
[REDACTED]	[REDACTED]	[REDACTED]
[REDACTED]	[REDACTED]	[REDACTED]
[REDACTED]	[REDACTED]	[REDACTED]
[REDACTED]	[REDACTED]	[REDACTED]

[REDACTED]

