3. STATISTICAL ANALYSES

3.1. General Considerations

All individual data will be listed as measured. All statistical summaries and analyses will be performed using SAS software (SAS Institute, Cary, North Carolina, USA).

All data from scheduled and unscheduled visits will be presented in the subject listings. However, unless noted otherwise, only data from scheduled/windowed visits will be included in the summaries, statistical analysis, and calculation of derived parameters.

Summary tables and listings (e.g., post text tables and individual subject data listings are prepared according to ICH Guideline E3) include a “footer” providing explanatory notes.

Continuous data will be summarized using an 8-point descriptive summary (n, mean, standard deviation, median, interquartile range [25% quartile, 75% quartile]), minimum, and maximum) unless otherwise specified.

Categorical data will be summarized using counts and percentages. Percentages will be shown to 1 decimal place and percentages for zero counts will be omitted.

For safety assessments, summary statistics will be reported by treatment.

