3.1.5. Actual Treatment

Data will be summarized by actual treatment group which will be determined by the treatment that was dispensed at the Day 1 visit.

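### Long-term dose is fixed by Maintenance treatment and remission status, so adverse event tables by Day 1 dose alone are confounded by both and can show a false dose pattern

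*SAP*

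**What the plan says.** SAP 1.2 gives the assignment rule.

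- In remission: subjects completing Maintenance "in clinical remission on active drug will continue with the same dose of TD-1473". For placebo, "Subjects entering the LTS Study after completing the Maintenance Study in clinical remission on placebo will be placed on 20 mg".
- Not in remission, including early exits for persistent loss of response or recurrent flare: "Subjects on 20 mg and 80 mg of TD-1473 will be dose-escalated one level up to 80 mg and 200 mg, respectively". Subjects already on 200 mg stay there. For placebo, "Placebo subjects entering the LTS Study not in remission will be dose escalated to 80 mg".

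On analysis, SAP 3.1 states: "For safety assessments, summary statistics will be reported by treatment". SAP 3.1.5 adds: "Data will be summarized by actual treatment group which will be determined by the treatment that was dispensed at the Day 1 visit". SAP 3.4.2 reports adverse events as numbers and percentages of subjects, and SAP 3.4.2.1 reports AESI incidence by category and preferred term. Neither uses Maintenance treatment or remission status. SAP 3.5.2 (subgroups) and SAP 3.2.1 (enrolment) are marked as not applicable to the synoptic report.

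The protocol did plan to describe the mix. Section 8.4.2 reads: "An enrollment summary will be provided showing the following counts by previous study treatment and clinical status at enrollment". Protocol 8.6.1.1 also starts the AESI time-to-event plots at the first TD-1473 dose ever rather than the first long-term dose, so it treats earlier exposure as relevant. SAP 3.4.2.1 does not carry those plots.

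**The concern.** The dose columns are not randomised groups. They differ systematically in two ways that could affect adverse event risk: whether the subject was on TD-1473 or placebo in Maintenance, and whether the disease was in remission at entry.

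Former placebo subjects start or restart TD-1473 at entry. Former TD-1473 subjects have already stayed on the drug through Maintenance or until loss of response or flare, and the inclusion criteria offer no route in for someone who left Maintenance because of an adverse event. It is therefore plausible, though not shown in the documents, that former placebo subjects have more early events. Non-remitters have active disease and possibly rescue medication, which could also raise event rates.

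Safety is the primary objective and no inferential tests are planned, so these descriptive tables are the main display of the primary endpoint. SAP 1.2 calls the design parallel-group, which invites side-by-side reading of the columns.

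**Working it through.** **Step 1. List the rule (SAP 1.2).**

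| Maintenance treatment | In remission | Not in remission |
|---|---|---|
| Placebo | 20 mg | 80 mg |
| 20 mg | 20 mg | 80 mg |
| 80 mg | 80 mg | 200 mg |
| 200 mg | 200 mg | 200 mg |

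Two facts follow without any assumption. No former placebo subject is on 200 mg. Within each remission stratum, all former placebo subjects are at the lowest dose used there: 20 mg for remitters, 80 mg for non-remitters. The 20 mg column contains only remitters.

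**Step 2. Composition.** Assume equal entry from the four arms and a common remission fraction r among entrants. Neither figure is in the documents.

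- Former placebo share: 20 mg, r/(2r) = 50%; 80 mg, (1 − r)/(2 − r); 200 mg, 0%.
- Non-remitter share: 20 mg, 0%; 80 mg and 200 mg, (2 − 2r)/(2 − r).

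For r from 0.1 to 0.5, the former placebo share at 80 mg runs from 47.4% to 33.3%, and the non-remitter share at 200 mg from 94.7% to 66.7%. At r = 0.4 they are 37.5% and 75%.

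**Step 3. Expected crude rates with no dose effect.** Let b be the risk in remitters formerly on TD-1473, s the excess for former placebo subjects and n the excess for non-remission. The documents state none of these, so b = 40% and s = 20 points are illustrative. Expected rate = b + s × (former placebo share) + n × (non-remitter share).

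| Scenario | n (points) | 20 mg | 80 mg | 200 mg |
|---|---|---|---|---|
| r = 0.4 in all arms | 0 | 50.0% | 47.5% | 40.0% |
| r = 0.4 in all arms | 10 | 50.0% | 55.0% | 47.5% |
| r = 0.4 in all arms | 20 | 50.0% | 62.5% | 55.0% |
| Remission 15% on placebo, 40% on active | 0 | 45.5% | 49.2% | 40.0% |
| Remission 15% on placebo, 40% on active | 20 | 45.5% | 64.9% | 55.0% |

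In the unequal scenario the former placebo shares are 0.15/0.55 = 27.3% at 20 mg, 0.85/1.85 = 45.9% at 80 mg and 0% at 200 mg.

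**Step 4. Where 200 mg and 20 mg cross.** The crude gap closes when n = s × (placebo share at 20 mg)/(non-remitter share at 200 mg).

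- r = 0.4 in all arms: 20 × 0.50/0.75 = 13.3 points.
- Unequal remission: 20 × 0.273/0.75 = 7.3 points.
- With a smaller s of 10 points and r from 0.5 to 0.1: 5/0.667 = 7.5 down to 5/0.947 = 5.3 points.

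In all the scenarios above 200 mg stays below 80 mg, provided s is positive.

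**Step 5. Which split recovers the null** (r = 0.4, s = 20, no dose effect).

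- *Remission status only, n = 0:* remitters show 50% at 20 mg against 40% at 80 and 200 mg; non-remitters show 50% at 80 mg against 40% at 200 mg. The false pattern remains.
- *Former TD-1473 subjects only, remission ignored:* non-remitters form 0%, 60% and 75% of the 20, 80 and 200 mg columns. With n = 10 this gives a false rise of 0, 6 and 7.5 points.
- *Former TD-1473 subjects within remission status:* 40% at every dose for remitters, and 40% + n at both 80 and 200 mg for non-remitters. This is the correct null.

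**The case against.** A reader might infer that the planned tables are tilted towards making higher doses look safer. The documents do not support that, for four reasons.

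- Remission status can push the other way: the 20 mg column has no non-remitters and the 200 mg column has many. Step 4 shows that a moderate non-remission excess cancels or reverses the 200 against 20 mg gap.
- A higher risk in former placebo subjects is an assumption. Entry requires clinical response in Induction, and the documents do not say what these subjects received then, so they cannot be called drug-naive.
- The hypersensitivity exclusion ("Develops hypersensitivity to excipients or contents of the study drug as noted in Protocol 0157") applies to every entrant, not only those heading for 200 mg. The two possibly related skin events in the 4-week Phase 1b study do not show clustering after starting drug.
- If some risks grow with cumulative exposure, former TD-1473 subjects carry more of them, and they make up the whole 200 mg column.

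It can also be said that the objective is the safety of TD-1473 rather than dose-response, that SAP 1.2 already discloses how dose is assigned, and that a synoptic report of a terminated study may have few subjects per cell.

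These points remove any claim about net direction and limit the importance of the issue. They do not make the columns comparable: two biases of unknown size do not reliably cancel, and disclosing the rule does not tell a reader of the tables how each column is made up.

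**Conclusion.** The concern holds as one of confounding, not of known direction. The composition of the columns follows exactly from SAP 1.2. Tables by Day 1 dose alone can therefore show a false dose pattern when dose has no effect.

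If starting or restarting TD-1473 raises adverse event risk, 200 mg looks safer within strata than the lowest dose used there. In the crude tables the direction for 200 against 20 mg is not determined, and 80 against 20 mg can go either way. The sizes shown, such as a 10-point gap between 20 and 200 mg at n = 0 and r = 0.4, rest on assumed risks, equal entry from the arms and assumed remission fractions. The actual group sizes after early termination are not given. The overall safety summary across doses is unaffected. This is a cheap improvement to how the dose columns are presented and read.

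**What to change.** - In SAP 3.4.2 and 3.4.2.1, present the overall adverse event summary and the AESIs by long-term dose, split by Maintenance treatment (placebo or TD-1473) and by remission status at entry. Do the same for TEAEs by SOC and PT where cell sizes allow.
- State in the SAP and in table footnotes that the dose columns are not randomised, and that doses are compared only among subjects who were on TD-1473 in Maintenance, within the same remission status. Former placebo subjects have only one dose per stratum, so they give no within-stratum dose comparison.
- Restore in SAP 3.2.1 the Protocol 8.4.2 counts by previous treatment and clinical status. These describe the mix but do not by themselves correct the AE tables.

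The cost is SAP wording and two added splits. Both variables already determine the dose, so no new data are needed. The downside is smaller cells; if they become too sparse, the counts and the non-randomised label are the minimum. Some non-comparability remains, because remission is itself an outcome of Maintenance and some 200 mg non-remitters are newly escalated, so the label should stay even with the split. No change to the dosing rule is implied.
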